11.2.3 Secondary Analyses

At each sampling time point, the actual value and the change from baseline for plasma α -Gal A activity, Gb3 and lyso-Gb3, eGFR, ejection fraction, global longitudinal strain, and LVMI and left ventricular systolic function will be summarized by dose and cohort using descriptive statistics and plotted over the 1-year study period by dose and cohort. Similar summaries will also be provided for ERT naïve/ERT pseudo-naïve subjects, and separately for ERT subjects (migalastat subjects will be grouped with either the ERT naïve/ERT pseudo-naïve subjects, or with the ERT subject, based on the clinical response determined by the Investigator at Screening).

For subjects who undergo ERT withdrawal, changes from pre- to post-ERT withdrawal in the frequency and dose of ERT infusions will be evaluated and summarized using annualized total dose and number of infusions. Duration of ERT withdrawal may also be analyzed.

Clearance of ST-920 measured by vg in the different samples (plasma, saliva, urine, stool, and semen, if applicable) will be summarized over time by dose and cohort.

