2. STUDY OBJECTIVES AND ENDPOINTS

2.1 Objectives and Endpoints

Objectives	Endpoints
Primary	

 To assess safety and tolerability of ST-920 	
 Incidence of treatment-emergent adverse events (TEAEs) Additional safety evaluations will include: 
 Routine hematology, chemistry, and liver tests, vital signs, electrocardiogram (ECG) and echocardiogram (ECHO) Serial alpha fetoprotein (AFP) testing and MRI of liver (or equivalent imaging modality) to monitor for liver mass
Secondary	

 To assess α-Gal A activity and the presence of its substrates in plasma over time 	
 Change from baseline at specific time points over the 1-year study period in: 
 α-Gal A activity in plasma Gb3 and lyso-Gb3 levels in plasma

 To assess impact of ST-920 on ERT administration required for subjects on ERT 	
 Change from baseline at specific time points over the 1-year study period in: 
 Frequency of ERT infusion

 To assess the impact of ST-920 on renal function 	
 Change from baseline at specific time points over the 1-year study period in: 
 Estimated glomerular filtration rate (eGFR) using the CKD-EPI formula

 To assess the impact of ST-920 on cardiac function and left ventricular hypertrophy 	
 Change from baseline at specific time points over the 1-year study period in: 
 Ejection fraction, global longitudinal strain, left ventricular mass index (LVMI), left ventricular systolic function measured by cardiac magnetic resonance imaging (CMR)

 To evaluate ST-920 vector DNA shedding over time 	
 ST-920 vector clearance measured by level of vector genome in blood (plasma), saliva, urine, stool, and semen (if applicable)
Exploratory	

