3.6 Enzyme Replacement Therapy Withdrawal (any time after Week 4)

The ultimate goal of ST-920 treatment is to abrogate the need for ERT by using an AAV2/6 vector encoding cDNA for human α -Gal A, resulting in long-term, liver-specific expression of α -Gal A in Fabry disease subjects. During dose escalation, subjects on ERT may be considered for complete withdrawal of ERT at the discretion of the Principal Investigator following consultation with the Sponsor and with agreement from the subject. The ERT withdrawal can only be considered after a period of four weeks, in order to allow enough time for transduction of the target liver cells.

Subjects who undergo ERT withdrawal will be closely monitored for any AEs, vital signs, any changes in safety laboratory evaluations, including liver tests and activity of α -Gal A and substrates (Gb3 and lyso-Gb3) compared to baseline ([Appendix 2](#)).

During dose escalation, ERT withdrawal is at the discretion of the Site Investigator after consultation with the Sponsor, and is only to be considered for subjects who are willing and meet all of the following criteria:

- Are ≥ 4 weeks post-administration of ST-920.
- Are medically stable and can tolerate temporary discontinuation of ERT in the judgment of the Site Investigator.

- Agree to increased safety monitoring and additional lab testing until ERT Withdrawal Follow-Up visit ([Appendix 2](#)).

Initiation of the dose expansion phase of the study assumes that a safe and tolerable dose of ST-920 has been achieved. At this point, ERT withdrawal will be implemented for all subjects who are in the expansion cohorts and have achieved supraphysiological (above normal range) plasma α -Gal A for 8 weeks \pm 2 weeks, at the discretion of the investigator.

ERT withdrawal assumes a complete stop in ERT administration rather than a “dose-down” or dose reduction.

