APPENDIX 2: ERT WITHDRAWAL SCHEDULE OF EVENTS

PROCEDURE*	ERT Withdrawal Visit (a)	ERT Withdrawal Monitoring Visits (+/- 2 days) (b)		ERT Withdrawal Follow-Up Visit (+/- 2 days) (c)
		Week 4	Week 8	Week 12
Physical Examination	X			X
Vital Signs (d)	X			X
Clinical Laboratory	X			X
Concomitant Medications	X	X	X	X
AE Assessment	X	X	X	X
ERT Administration Log		X	X	X
Liver Panel (e)	X	X	X	X
α -Gal A Testing (f)	X	X	X	X
Gb-3 Testing (f)	X	X	X	X
Lyso Gb-3 Testing (f)	X	X	X	X
eGFR	X	X	X	X
Urine pregnancy test	X	X	X	X
ERT Clinical Assessment				X

* Assessments associated with ERT withdrawal that are duplicated at regularly scheduled study visits may be waived if visits are combined ([Appendix 1](#)).

- ERT Withdrawal visit may occur at any time after the Week 4 visit (refer to [Section 3.6](#) for additional guidance).
- ERT Withdrawal Monitoring visits will occur on Week 4 and Week 8 \pm 2 days after the ERT withdrawal visit. ERT Withdrawal Monitoring visits have assessments that do not require evaluation at the clinical site and may therefore be conducted remotely. Assessments for AEs and concomitant medications may be conducted by study staff over the phone.
- The ERT Withdrawal Follow-Up visit will occur at Week 12 \pm 2 days after the ERT withdrawal visit but can occur earlier at the discretion of the Site Investigator, if clinically indicated. However, ERT may be re-initiated at any time based on clinical circumstances or at the judgment of the Investigator.
- Vital signs include height, weight, systolic/diastolic blood pressure, heart rate, respiratory rate, and temperature; refer to the Study Reference Manual.
- Liver panel (including assessment of AST, ALT, GGT, total and direct bilirubin, ALP, LDH, albumin, and total protein levels) does not need to be drawn as a separate sample if Clinical Laboratory Tests are obtained at the same visit.
- Subjects must be able to provide additional samples for α -Gal A, Gb3, and lyso-Gb3 testing.

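### The ERT-frequency endpoint is defined for all subjects on ERT but analysed only in those who stop ERT, so the planned figure does not depend on how many could stop

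*Combined protocol and SAP*

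**What the plan says.** The secondary objective in Section 2.1, repeated in the synopsis, is "To assess impact of ST-920 on ERT administration required for subjects on ERT". Its endpoint is change from baseline at specific time points over the one-year study period in "Frequency of ERT infusion".

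Section 11.2.3, with matching text in the synopsis, gives one analysis. It covers a subset and uses a different contrast: "For subjects who undergo ERT withdrawal, changes from pre- to post-ERT withdrawal in the frequency and dose of ERT infusions". The measures are the infusion count and the total dose, each expressed per year. The section adds that "Duration of ERT withdrawal may also be analyzed".

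Section 3.6 defines the subset. "ERT withdrawal assumes a complete stop in ERT administration rather than a" stepped reduction. "During dose escalation, ERT withdrawal is at the discretion of the Site Investigator after consultation with the Sponsor", for willing and medically stable subjects at least four weeks after dosing. In expansion, withdrawal applies to subjects whose plasma enzyme activity has been above the normal range for about 8 weeks, again at the investigator's discretion. On timing, Appendix 2 says "ERT Withdrawal visit may occur at any time after the Week 4 visit". Section 3.6 also allows ERT to be restarted at any time and an unsuccessful withdrawal to be repeated.

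**The concern.** The analysis changes both parts of the endpoint. The population goes from subjects on ERT to those who withdraw, and the reference goes from baseline to the time before withdrawal. Membership of the analysed group is settled after dosing, partly by discretion and, in expansion, by enzyme response. Subjects on ERT who never stop contribute nothing.

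No other planned summary fills the gap. The separate summaries for ERT subjects in Section 11.2.3 concern enzyme, substrate, renal and cardiac measures. Section 11.2.1 counts enrolment, dosing, discontinuation and completion, not ERT status. No proportion withdrawing or ERT-free is planned, and time off ERT is optional.

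Section 3.6 calls ending the need for ERT the ultimate goal of the treatment, and Section 6.4.1 expects most subjects to be on ERT at baseline. As written, the summary could not distinguish a dose at which few ERT subjects stop from one at which nearly all do.

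**Working it through.** The plan states no figure for this endpoint, so there is none to reproduce. The check compares the planned summary with one that follows Section 2.1.

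**Inputs from the protocol.** ERT every 14 days (Section 7.2), so about 52/2 = 26 infusions a year; follow-up to Week 52; withdrawal is a complete stop (Section 3.6).

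**Assumptions.** The protocol does not give the share *p* of ERT subjects who withdraw, the withdrawal week *W*, or the restart pattern. These are varied below. Non-withdrawers are taken to stay at 26 a year.

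**Planned summary, one withdrawer.** If the window runs to Week 52 and resumed infusions count, reduction = weeks off ERT / (52 - *W*).

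- No restart: (52 - *W*)/(52 - *W*) = 100% for any *W*.
- Stop at Week 8, resume 12 weeks later: 12/44 = 27.3%.
- Stop at Week 24, resume 12 weeks later: 12/28 = 42.9%.

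If the window ended at restart, each of these would be 100% by construction. The plan does not say which window applies.

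**Planned summary, mean over withdrawers** (all stop at Week 8, a fraction *f* resumes 12 weeks later): (1 - *f*) × 100% + *f* × 27.3%.

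- *f* = 0.25: 81.8%.
- *f* = 0.50: 63.6%.

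Neither formula contains *p*. For a given pattern among withdrawers, the result is the same however many ERT subjects withdraw.

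**All subjects on ERT, 52 weeks, no restarts.** Mean infusions = *p* × *W*/2 + (1 - *p*) × 26.

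| *p* | *W* | Mean infusions | All-ERT change | Withdrawers only |
|---|---|---|---|---|
| 0.5 | 24 | 0.5 × 12 + 0.5 × 26 = 19.0 | -26.9% | -100% |
| 0.3 | 24 | 0.3 × 12 + 0.7 × 26 = 21.8 | -16.2% | -100% |
| 0.5 | 40 | 0.5 × 20 + 0.5 × 26 = 23.0 | -11.5% | -100% |

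**Extremes**, assuming 20 subjects on ERT, withdrawal at Week 8 and no restart: the all-ERT reduction is *p* × 44/52. That is 4.2% if 1 of 20 withdraws and 84.6% if all 20 do. The planned summary gives 100% in both cases.

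**With restarts**, if half of the withdrawers resume at 12 weeks: mean time off ERT among withdrawers is 0.5 × 44 + 0.5 × 12 = 28 weeks. The all-ERT reduction is 0.5 × 28/52 = 26.9% if 10 of 20 withdraw and 28/52 = 53.8% if all 20 do. The planned summary gives 63.6% in both cases.

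**The case against.** A reader might infer that the planned figure must come out near 100%. The documents do not support that. The analysed group is everyone who undergoes withdrawal, including those who restart; restarts and repeat attempts are foreseen; and a visit 12 weeks after withdrawal exists to decide on resumption. If resumed infusions count, the figure can be far below 100%.

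Nor is staying on ERT simply treatment failure. In escalation, withdrawal needs a willing subject and an investigator's decision, with no response criterion, so a responder may remain on ERT. An all-ERT average mixes need, discretion and timing. The working shows this: 30% withdrawing at Week 24 gives -16.2%, a larger reduction than the -11.5% from half withdrawing at Week 40. That stands, and it is why the average cannot be reported alone.

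Two further criticisms are tempting but not established. The pre-withdrawal reference period may include time after ST-920, but subjects are to stay on a stable 14-day regimen until they withdraw, so no bias is shown. Annualising could give undue weight to short windows, but the plan does not say how individual rates are combined.

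It can also be said that Section 11.2 leaves detail to a SAP, and that Section 6.1.8 says ERT frequency will be studied before and after ST-920. But Section 11.2.3 already fixes the restricted population, and the supplied document contains no SAP text on this endpoint that widens it. Section 6.1.8 secures the data without specifying a summary.

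**Conclusion.** The concern holds as a mismatch between endpoint and analysis. Followed as written, the plan yields a figure for withdrawers alone that is independent of the share of ERT subjects who stop: 100% with no restarts, lower if restarts are counted. The corresponding all-ERT change would be -27% or -16% in the two Week 24 scenarios. Those sizes rest on 26 infusions a year, no restarts, and assumed withdrawal shares and times. The independence from the share withdrawing does not rest on them.

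Severity is moderate. All summaries are descriptive, the endpoint is secondary, and no error rate, sample size or dose-escalation rule depends on it. What is affected is the interpretation of the result.

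**What to change.** In Section 11.2.3 and the synopsis:

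1. Make the main summary all dosed subjects on ERT at baseline. Compare ERT infusions and total dose per unit time before ST-920 with the whole period from ST-920 to Week 52, by dose and cohort. Non-withdrawers and restarters contribute what they received.
2. Beside it, report the number and proportion who withdraw and who are ERT-free at Week 52, over the on-ERT denominator.
3. State that resumed infusions and all withdrawal attempts count.
4. Keep the withdrawers-only table as supportive.

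No change to the withdrawal or restart rules is implied, and no new data are needed: the ERT Administration Log (Section 6.1.8) records every dose from screening. The cost is a wording change and a little extra analysis. The resulting figure will probably look less favourable. If non-withdrawers keep their usual rate and resumed infusions count, the all-ERT reduction, *p* × weeks off / 52, is always below the withdrawers-only figure, weeks off / (52 - *W*).

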11.2.4 Exploratory Analyses

Data permitting, the following exploratory endpoints and their change from baseline summaries by dose and cohort will be provided at each sampling time point over the 1-year study period:

- LGE, native myocardial T1 values and T2 mapping measured by CMR
- High sensitivity troponin T, NT-proBNP and other cardiac biomarkers
- MLHF-Q summary score
- UPCR and UACR
- Biomarkers of renal function in urine
- Neuropathic pain measured by the BPI
- Frequency of pain medication use
- GI symptoms measured by the GI symptoms rating scale
- MSSI
- QOL patient-reported outcome measured by the SF-36 questionnaire
- α -Gal A activity measured in skin

- Gb3 inclusion levels measured in skin in ERT-naïve and ERT-pseudo-naïve subjects and selected subjects previously on migalastat
- Gb3 and lyso-Gb3 urine for all subjects over time
- Pulmonary function over time
- Audiologic function over time

Data permitting, summaries of percent reduction from baseline at Week 24 by dose and cohort will be provided for:

- Gb3 inclusion in the kidney (assessed by kidney biopsy) in ERT-naïve and ERT-pseudo-naïve subjects and selected subjects previously on migalastat

Summaries by dose and cohort will be provided for the following exploratory endpoints at each sampling time point:

- Measurement of antibodies to AAV2/6
- Assessment of cell-mediated immune response to AAV2/6
- Measurement of immune response to α -Gal A

APPENDIX 1: SCHEDULE OF EVENTS

PROCEDURE	Screening	Baseline (a)	Health Care Facility		Day	Week																	ETV
					8	2	4	6	8	12	16	20	24	28 *	32 *	36	40*	44 *	48*	52 EOS			
	(w/in 8 weeks of Baseline)	(w/in 12 weeks prior to ST-920 infusion)	Day 1	Day 2	(+/- 1 day)	(+/ -2 days)				(+/ -1 week)				(+/-2 weeks)	(+/ -1 week)					(-2 weeks/+ 1 month)			
Informed Consent	X																						
Medical History	X																						
Inclusion/Exclusion	X																						
Demographics	X																						
Fabry Gene Sequencing (b, c)	X																						
Infectious Disease Screening	X																						
Neutralizing Antibodies to AAV2/6 (d)	X																						
Physical Examination	X	X	X	X	X		X		X	X			X			X				X	X		
Vital Signs (e)	X	X	X	X	X	X	X	X	X	X	X	X	X			X				X	X		
Concomitant Medications	X	X	X	X	X	X	X	X	X	X	X	X	X	X	X	X	X	X	X	X	X		
Clinical Laboratory (f)	X	X	X (g)	X		X	X	X	X	X	X	X	X			X				X	X		
AE Assessment	X	X	X	X	X	X	X	X	X	X	X	X	X	X	X	X	X	X	X	X	X		
ERT Administration Log	X	X	X		X	X	X	X	X	X	X	X	X	X	X	X	X	X	X	X	X		
Liver Panel (h)	X	X (i)	X (g)	X									X	X	X	X	X	X	X	X	X		
12-Lead ECG	X	X			X								X							X	X		
ECHO (b)	X																			X	X		
MRI of Liver (b, j)	X												X							X	X		
eGFR (k)	X	X			X		X		X	X	X	X	X	X	X	X	X	X	X	X	X		
Diagnostic α-Gal A Testing (l)	X																						
α-Gal A Testing in Blood (m)	X	X (n)				X (o)							X	X	X	X	X	X	X	X	X		
Gb3 and lyso-Gb3 Testing (m)	X	X (n)		X (o)									X	X	X	X	X	X	X	X	X		
Iron panel (p)		X																					
Biomarkers of Renal Function in Urine	X	X							X	X			X			X				X	X		

APPENDIX 1: SCHEDULE OF EVENTS (continued)

PROCEDURE	Screening	Baseline e (a)	Health Care Facility		Day	Week																ET V
					8	2	4	6	8	12	16	20	24	28 *	32 *	36	40 *	44 *	48 *	52 EOS		
	(w/in 8 weeks of Baseline)	(w/in 12 weeks prior to ST-920 infusio n)	Day 1	Day 2	(+/- 1 day)	(+/ -2 days)				(+/ -1 week)				(+/ -2 weeks)		(+/ -1 week)					(- 2weeks /+1 month)	
Protein and albumin to Creatinine Ratio in Urine	X	X								X			X			X				X	X	
Cardiac MRI (CMR) (g)	X	X											X							X	X	
Blood samples for high sensitivity troponin T, NT- proBNP, and other cardiac biomarkers		X							X	X			X			X			X	X	X	
Minnesota Living With Heart Failure Questionnaire (MLHF-Q) (r)		X											X							X	X	
Circulating AFP	X						X		X	X			X							X	X	
Skin Biopsy (s)		X											X							X	X	
PT, PTT & INR (t)		X											X									
Kidney biopsy (t)		X											X									
Frequency of Pain Medication Use	X	X				X	X	X	X	X	X	X	X	X	X	X	X	X	X	X	X	
Short Form Brief Pain Inventory (BPI)		X								X			X			X				X	X	
QOL (SF-36 Questionnaire)		X											X							X	X	
GI Symptoms Rating Scale		X											X							X	X	
Mainz Severity Score Index		X											X							X	X	
PFTs (b)	X	X											X							X	X	
Audiologic Evaluation		X																		X	X	
Vector Genome PCR in Blood (Plasma)				X (12 hr post- infusi on)																		

APPENDIX 1: SCHEDULE OF EVENTS (continued)

Vector Genome PCR in Blood (Plasma), Saliva, Urine, Stool and Semen (u)		X			X	X	X		X	X	X	X	X			X			X	
AAV Immunogenicity (v)		X					X	X		X		X			X				X	
Immune response to α -Gal A (m)	X	X					X		X	X	X	X			X				X	X
Future Research (optional) (w)	X	X					X	X	X	X	X	X	X	X	X	X	X	X	X	X
ST-920 Infusion			X																	
COVID-19 Assessment (x)	X	X	X	X	X	X	X	X	X	X	X	X	X	X	X	X	X	X	X	X
Pregnancy test (if applicable) (y)	X	X	X				X		X	X	X	X	X	X	X	X	X	X	X	X

- * Week 28, 32, 40, 44, and 48 study visits have assessments that do not require evaluation at the clinical site, and therefore may be conducted remotely. Assessments for AEs and concomitant medications may be conducted remotely over the phone by the study staff.
- For subjects in screening or baseline whose visits are impacted by the COVID-19 situation, the duration of baseline can be extended up to 24 weeks without having to be screen -failed. The Investigator will discuss with Sangamo Medical Monitor to decide which tests need to be repeated to continue in the study on a case-by-case basis.
 - Assessments including ECHO, PFTs, and MRI of liver performed within 6 months of consent may be used for evaluation of inclusion/exclusion criteria on a --case-by-case basis at the judgment of the Site Investigator. Further, genetic marker analysis including Fabry disease gene sequencing will not be repeated as these will not change over time.
 - The assay will be performed on blood or saliva samples. If available, gene sequencing results obtained prior to the study may be used.
 - If dosing is not completed within 12 weeks of sample collection, the serum neutralization assay to AAV6 should be repeated.
 - Vital signs include height, weight, systolic/diastolic blood pressure, heart rate, respiratory rate, and temperature. For frequency, refer to the Study Reference Manual. Baseline weight obtained 2-4 weeks prior to ST-920 infusion should be used for dose calculation.
 - Clinical laboratory tests include hematology, urinalysis, and serum chemistry.
 - On Day 1, clinical laboratory tests and liver panel should be drawn prior to ST-920 infusion.
 - Liver panel does not need to be drawn as a separate sample if Clinical Laboratory Tests are obtained at the same visit. Liver panel (including assessment of AST, ALT, GGT, total and direct bilirubin, ALP, LDH and albumin) and total protein levels will be performed twice weekly from Week 1 through Week 20 after ST-920 infusion, weekly for four weeks (Weeks 21, 22, 23, 24 [± 2 days]) and then monthly thereafter. Samples may be drawn tandemly for ALT, AST, ALP, and total bilirubin at either local or central labs with results to be utilized for decision on corticosteroid treatment. Liver tests may be conducted remotely and analyzed locally or centrally. If there is a need to initiate treatment with corticosteroids because of elevated ALT, liver enzymes will continue to be assessed at least twice a week until normalization and then per protocol thereafter analyzed locally or centrally.
 - The liver panel test for the baseline visit will be performed within 7-14 days of planned ST-920 dosing.
 - MRI or equivalent imaging modality for detection of liver masses.
 - eGFR calculated by creatinine levels in blood using the CKD-EPI formula.
 - This assay will be performed on plasma. If available, α -Gal A activity documentation obtained prior to the study may be used (plasma and leukocyte results are acceptable). For subjects who do not have a documented α -Gal A activity for diagnosis, a blood sample should be taken to measure plasma α -Gal A activity. For those subjects who are on ERT, this blood draw must be taken at least 14 days (± 1 day) after their last ERT infusion.
 - For subjects on ERT, α -Gal A, immune response to α -Gal A, Gb3 and lyso-Gb3 samples should be obtained at trough, defined as 14 days (+/- 1 day) after the previous ERT administration, and should be taken at the same time of the day (i.e. morning) as the subsequent enzyme and substrate samples in the study.

- n) 2 samples will be taken at baseline on 2 different occasions at least 13 days apart (for subjects on ERT, preferably at the same time during the day [e.g. in the morning] and at ERT trough levels, defined as 14 days [\pm 1 day] after the previous ERT administration).
- o) Samples will be taken every 2 weeks during the first 20 weeks after ST-920 infusion. For substrates analysis in urine, whether naive or on ERT, all samples should be collected in the morning (morning void). Samples may be collected remotely.
- p) Iron panel will include iron, ferritin, total iron binding capacity, transferrin saturation and hepcidin
- q) CMR can be done at screening or baseline. Results of a CMR completed within 6 months prior to consent can be used for screening or the baseline measure unless the parameters do not meet imaging guidelines. For all subjects, CMR will include LGE, T1 and T2 mapping.
- r) These assessments will be performed only for subjects enrolled in cardiac cohort.
- s) Unless contraindicated by a Site Investigator or physician.
- t) Kidney biopsies will be voluntary for Cohort 2 and mandatory for subsequent cohorts and performed on ERT-naïve or ERT-pseudo-naïve subjects (defined as not having received ERT treatment during the 6 months prior to baseline) and selected subjects previously on migalastat who the Principal Investigator, in conversation with the Sponsor Medical Monitor, considers a non-responder to migalastat based on clinical and/or biochemical assessments only, unless contraindicated by a Site Investigator or physician. In subjects who will have a kidney biopsy, PT, PTT & INR will be done locally prior to kidney biopsy to ensure blood coagulation is normal.
- u) Each type of sample (blood, saliva, urine, stool, semen [if applicable]) should be collected until 3 consecutive specimens of that sample type are reported as negative or undetectable for vector genome.
- v) Samples for AAV immunogenicity will be taken at baseline, and Weeks 4, 12, 24, 36, and 52 to measure total antibodies to AAV6. Additional samples for cell-mediated immunogenicity will be collected at baseline, Week 6 and when ALT is elevated or when there is a 50% drop in α -Gal A expression and/or prior to initiation of a corticosteroid treatment if possible.
- w) Future research specimens include plasma and serum.
- x) Subject must be fully vaccinated at least one month before infusion with ST-920. COVID-19 Assessments will be performed as outlined in [Appendix 7](#).
- y) Serum pregnancy test should be performed by the central laboratory at Screening. At other visits, a urine pregnancy test should be performed by the local laboratory or Investigator.

